## 7.2. Immunogenicity

Serum samples will be obtained for immunogenicity testing as follows:

- For subjects assigned to the Day 1, 8, and 30 regimen, on Day 1, Day 8, Day 15, Day 30, Day 37, Month 2, Month 4, Month 7, and Month 13.
- For subjects assigned to the Month 0, 1, and 6 regimen, on Day 1, Day 30, Day 37, Month 2, Month 6, Day 187, Month 7, Month 12, and Month 18.
- During the extension stage: at the fourth dose (immediately before the fourth dose), on Days 8 and 30 after the fourth dose, and at Months 6, 12, 18, 24, 30, and 36 after the fourth dose.

Both toxin A– and toxin B–specific neutralizing antibody levels will be measured. A minimum of 10 mL and up to 20 mL of blood will be collected (prior to vaccination if at a vaccination visit) for each measurement to allow for adequate volume required for repeat testing or additional antigen-specific immunogenicity testing to be performed.

An additional blood sample of approximately 40 mL will be obtained at Visit 6 (Month 2) for subjects on the Day 1, 8, and 30 regimen and Visit 4 (Month 2) for subjects on the Month 0, 1, and 6 regimen for use in development, qualification, and validation of *C difficile* serologic assays and reagents.

An additional optional whole blood sample of approximately 20 to 50 mL will be obtained from subjects at designated sites for exploratory purposes as follows:

- Designated sites participating in the month regimen will be asked to obtain additional blood samples from subjects who have signed an additional ICD for this procedure at Visit 12 for exploratory purposes.

Refer to the SRM for details regarding serum sample management and storage.

**7.3. CCI**

CCI

## **8. ADVERSE EVENT REPORTING**

### **8.1. Adverse Events**

All observed or volunteered AEs regardless of vaccine group or suspected causal relationship to the investigational product(s) will be reported as described in the following sections.

For all AEs, the investigator must pursue and obtain information adequate both to determine the outcome of the AE and to assess whether it meets the criteria for classification as an SAE requiring immediate notification to Pfizer or its designated representative. For all AEs, sufficient information should be obtained by the investigator to determine the causality of the AE. The investigator is required to assess causality. Follow-up by the investigator may be required until the event or its sequelae resolve or stabilize at a level acceptable to the investigator, and Pfizer concurs with that assessment.

As part of ongoing safety reviews conducted by the sponsor, any nonserious AE that is determined by the sponsor to be serious will be reported by the sponsor as an SAE. To assist in the determination of case seriousness, further information may be requested from the investigator to provide clarity and understanding of the event in the context of the clinical study.

### **8.2. Reporting Period**

For SAEs, the active reporting period to Pfizer or its designated representative begins from the time that the subject provides informed consent, which is obtained prior to the subject's participation in the study, ie, prior to undergoing any study-related procedure and/or receiving investigational product, through and including Visit 8 (Month 7 for subjects on the Day 1, 8, and 30 regimen and Month 12 for subjects on the Month 0, 1, and 6 regimen).

During the extension stage, the active reporting period for SAEs to Pfizer or its designated representative begins from the time that the subject provides informed consent for the extension stage, which is obtained prior to the subject's participation in the extension stage, ie, prior to undergoing any study-related procedure and/or receiving investigational product, through and including Visit 12 (6 months after the fourth dose).

SAEs occurring to a subject after the active reporting period has ended should be reported to the sponsor if the investigator becomes aware of them; at a minimum, all SAEs that the investigator believes have at least a reasonable possibility of being related to investigational product are to be reported to the sponsor.

All AEs should be recorded on the CRF from the time the subject provides informed consent until 1 month after the third vaccination (Visit 6 [Month 2] for subjects on the Day 1, 8, and 30 regimen and Visit 7 [Month 7] for subjects on the Month 0, 1, and 6 regimen).

During the extension stage, all AEs should be recorded on the CRF from the time the subject provides informed consent until 1 month after the fourth vaccination (Visit 11).

Any AE occurring up to 48 hours after each subsequent blood draw (Visit 6 [Month 2], Visit 7 [Month 4], Visit 8 [Month 7], and Visit 9 [Month 13] for subjects on the Day 1, 8, and 30 regimen and Visit 7 [Month 7], Visit 8 [Month 12], and Visit 9 [Month 18] for subjects on the Month 0, 1, and 6 regimen) must be recorded on the CRF.

During the latter part of the extension stage, any AE (including RRIs) occurring up to 48 hours after the blood draw at Visits 12, 13, 14, 15, 16, and 17 (Months 6, 12, 18, 24, 30, and 36 after the fourth dose) must be recorded on the CRF.

The investigator is required to assess whether the AE may be related to the subject's participation in the study.

CCI

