### 2.2.2. Primary Safety Endpoints

- Numbers and proportions of subjects reporting local reactions (pain, erythema, and induration) and their severity, as self-reported on e-diaries for up to 14 days following Vaccinations 1, 2, and 3.
- Numbers and proportions of subjects reporting systemic events (fever, vomiting, diarrhea, headache, fatigue, new or worsening muscle pain, and new or worsening joint pain) and their severity, as self-reported on e-diaries for up to 14 days following Vaccinations 1, 2, and 3.
- Numbers and proportions of subjects reporting AEs from the first vaccination up to 28 days after the third vaccination categorized according to the Medical Dictionary for Regulatory Activities (MedDRA).
- Numbers and proportions of subjects reporting SAEs from the first vaccination until 6 months after the third dose of vaccine, categorized according to MedDRA.

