#### **2.2.4. Secondary Safety Endpoints**

- Numbers and proportions of subjects reporting local reactions (pain, erythema, and induration) and their severity, as self-reported on e-diaries for up to 14 days following the fourth vaccination.
- Numbers and proportions of subjects reporting systemic events (fever, vomiting, diarrhea, headache, fatigue, new or worsening muscle pain, and new or worsening joint

pain) and their severity, as self-reported on e-diaries for 14 days following the fourth vaccination.

- Numbers and proportions of subjects reporting AEs from the time of the fourth vaccination up to 28 days after the fourth vaccination categorized according to the Medical Dictionary for Regulatory Activities (MedDRA).
- Numbers and proportions of subjects reporting SAEs from the time of the fourth vaccination until 6 months after the fourth dose of vaccine, categorized according to MedDRA.

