#### **6.1.8. Visit 8: Month 7 (165 to 195 Days After Visit 4)**

- Ensure that the subject continues to be eligible for the study and does not meet any of the withdrawal criteria as described in [Section 6.5](#).
- Based on clinical evaluation, determine whether any newly diagnosed chronic medical conditions or SAEs have occurred since the last study visit. Record and report findings as described in [Section 8](#) and the [Schedule of Activities](#). Review AEs that were ongoing from the previous visit and record their stop dates or confirm if they are still continuing. In addition, any AEs occurring up to 48 hours after the blood draw will be recorded.
- Conduct a targeted physical examination, including vital signs if appropriate, evaluating any clinically significant abnormalities based on history and the participant's self-reported symptoms or complaints since the last visit.
- Collect a blood sample of approximately 20 mL for immunogenicity testing ([Section 7.2](#)).
- Ask the subject to contact the site staff or investigator immediately if any significant illness or hospitalization occurs.
- Schedule an appointment for the subject to return for the next study visit.
- Complete the source documents.
- Complete the CRF.

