### **6.3.3. Visit 11: Day 30 After Vaccination 4 (25 to 35 Days After Visit 9)**

- Review the subject's e-diary data after Dose 4 and follow up on any ongoing local reactions or systemic events.
- Collect the subject's e-diary.
- Ensure that the subject continues to be eligible for the study (see [Section 6.5](#)).
- Based on clinical evaluation, determine whether any AEs or SAEs have occurred since the last study visit. Record and report findings as described in [Section 8](#) and the [Schedule of Activities](#). Review AEs that were ongoing from the previous visit and record their stop dates or confirm if they are still continuing.
- Record nonstudy vaccines and concomitant medications as described in [Section 5.8.1](#).
- Conduct a targeted physical examination, including vital signs if appropriate, evaluating any clinically significant abnormalities based on history and the participant's self-reported symptoms or complaints since the last visit. Abnormal results, including those that indicate worsening of medical history conditions, must be recorded on source documents and the AE CRF (with recording of time relative to vaccination) as appropriate.
- Collect a blood sample of approximately 20 mL for immunogenicity testing ([Section 7.2](#)).

- Ask the subject to contact the site staff or investigator immediately if any significant illness or hospitalization occurs.
- Schedule an appointment for the subject to return for the next study visit.
- Complete the source documents.
- Complete the CRF.

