#### **6.3.5. Visit 13: Month 12 After Vaccination 4 ( $\pm 30$ Days)**

- Ensure that the subject continues to be eligible for the study (see [Section 6.5](#)).
- Record any AEs or RRIs that occurred up to 48 hours after the previous blood draw as described in [Section 8](#) and the [Schedule of Activities](#). Review any AEs that were ongoing from the previous visit and record their stop dates or confirm if they are still continuing.

- Collect a blood sample of approximately 20 mL for immunogenicity testing ([Section 7.2](#)).
- Schedule an appointment for the subject to return for the next study visit.
- Complete the source documents.
- Complete the CRF.

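### Active SAE reporting ends at Visit 8 and Visit 12, whose windows open before the 6-month SAE endpoints close, so a compliant early visit can leave up to 13 or 28 days not actively covered

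*Protocol*

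**What the plan says.** **Endpoints.** Protocol 2.2.2 lists as a primary safety endpoint "Numbers and proportions of subjects reporting SAEs from the first vaccination until 6 months after the third dose of vaccine". Protocol 2.2.4 sets the extension-stage counterpart: "Numbers and proportions of subjects reporting SAEs from the time of the fourth vaccination until 6 months after the fourth dose of vaccine". SAP 3.1.2 and 3.2.2 repeat both periods. Neither document converts 6 months into days.

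**End of active collection.** Protocol 8.2 stops active SAE reporting at Visit 8 for the first three doses. For the fourth it runs "through and including Visit 12 (6 months after the fourth dose").

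**Visit windows.** The day regimen has "Visit 8: Month 7 (165 to 195 Days After Visit 4"). Visit 8 of the month regimen has the same 165 to 195 days, counted from its own third dose (6.2.8). Visit 12 is Month 6 after Vaccination 4, plus or minus 30 days (6.3.4).

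**What follows each visit.**
- Visits 8 and 12: AEs up to 48 hours after the blood draw are recorded (6.1.8, 6.2.8, 6.3.4, 8.2).
- After the active period: SAEs are to be reported if the investigator learns of them (8.2).
- Visit 8: subjects are told to contact the site about significant illness or hospitalization. The Visit 12 list has no such instruction.
- Visit 9, subjects not entering the extension: no SAE entry in the schedule and no SAE question in 6.1.9 or 6.2.9. For those entering, active SAE reporting restarts at extension consent.
- Visit 13: "Record any AEs or RRIs that occurred up to 48 hours after the previous blood draw".

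**Analysis.** SAP 6.1.2 and 6.2.2 report numbers, proportions and 95% CIs, with no allowance for length of follow-up. SAP 6.2.2 gives the Dose 4 SAE period as 28 days, against 6 months in SAP 3.2.2 and Protocol 2.2.4.

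**The concern.** The endpoint is a period of time, while collection stops at an appointment. Where the appointment may fall before the period ends, a subject can comply fully and still have days at the end that no one actively asks about. If the SAE table counts events to a fixed day with every vaccinated subject in the denominator, that subject counts as event-free over those days.

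The Dose 3 SAE proportion is a primary safety endpoint, and the 6-month post-Dose 3 analysis is meant to support regulatory interactions (Protocol 9.4.4). The Dose 4 gap is wider and less protected: there is no hospitalization prompt at Visit 12, no targeted examination at Visit 12 or 13, and Visit 13 looks back only to the 48 hours after the previous draw.

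The Dose 4 blind is tied to the same pair of markers. Protocol 5.2 and 5.3 hold it until Visit 12 and describe that visit as 6 months after the dose, although the two can lie 30 days apart.

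**Working it through.** **The plan's own figure.** The documents give no figure for follow-up shortfall. The nearest is Protocol Table 8: with a true rate of 1.0% and 183 subjects, the chance of at least one event is 0.84. Check: 1 − (1 − 0.01)^183 = 0.841. It reproduces.

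**Inputs.** Visit 8 on days 165 to 195 after Dose 3 (31 possible days). Visit 12 at Month 6 ± 30 days, which is days 150 to 210 if 6 months is 180 days (61 possible days). Two further days from the 48-hour rule, since an SAE is an AE. Assumptions that are mine: T = 180 days, with 183 as a check; visit days evenly spread; a constant event rate; a cut at day T; nothing captured later.

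**Formula.** Shortfall for a visit on day d = max(0, T − (d + 2)). Relative loss = mean shortfall ÷ T.

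**Visit 8, T = 180.** Days 165 to 177 are short, so 13/31 = 42%. The largest gap is 180 − 167 = 13 days. The gaps sum to 13 × 14 / 2 = 91, so the mean is 91/31 = 2.9 days and the loss 2.9/180 = 1.6%. With T = 183: 16/31 = 52% short, largest gap 16 days, mean 136/31 = 4.4 days (2.4%).

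**Visit 12, T = 180.** Days 150 to 177 are short, so 28/61 = 46%. The largest gap is 180 − 152 = 28 days. The gaps sum to 28 × 29 / 2 = 406, so the mean is 406/61 = 6.7 days and the loss 6.7/180 = 3.7%. The largest gap stays 28 days for any day count, because the window is set around Month 6 itself.

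**Without the 48-hour rule (T = 180).** Visit 8: 15/31 = 48%, at most 15 days, mean 3.9 days (2.2%). Visit 12: 30/61 = 49%, at most 30 days, mean 7.6 days (4.2%). These are upper versions, because the rule is written for both visits.

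**Effect on a 1.0% rate.** Losing 1.6% gives 0.984%, and losing 3.7% gives 0.963%. The Table 8 probability becomes 0.836 or 0.830. If every subject came on the first permitted day, the losses are 13/180 = 7.2% and 28/180 = 15.6%, and the probabilities 0.818 and 0.788.

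**The other reading.** If the endpoint means to the visit, both windows centre on day 180 and the mean net shortfall is 0 days (3 days for Visit 8 if 6 months is 183 days). Follow-up still differs between subjects by up to 30 days at Visit 8 and 60 days at Visit 12.

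**28-day AE endpoints.** For Dose 3 the period is "Numbers and proportions of subjects reporting AEs from the first vaccination up to 28 days after the third vaccination". Visits 6 (day regimen) and 7 (month regimen) fall on days 25 to 35 and carry the 48-hour rule, so only a day-25 visit is short: 28 − 27 = 1 day, 1/11 = 9% of visit days, mean loss 0.3%. After Dose 4 the closing visit is "Visit 11: Day 30 After Vaccination 4 (25 to 35 Days After Visit 9"), for which 8.2 lists no 48-hour rule: at most 28 − 25 = 3 days, 3/11 = 27%, mean 6/11 = 0.55 days (1.9%). This concerns nonserious AEs only, since active SAE reporting continues to Visit 12.

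**The case against.** The strongest reply is that the protocol treats the visit and the time point as the same thing. Section 8.2 glosses Visit 12 as 6 months after the fourth dose, and 9.4.4 equates Month 7 and Month 12 with 6 months post-Dose 3. On that reading late visits add what early visits lose, and no net deficit is expected. This stands as far as it goes: a reader might infer that the SAE proportions are biased downward, but that needs a fixed-day cut and no late capture, and neither document states the first. The reply does leave subjects contributing unequal follow-up to one proportion.

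A reader might also infer that a large share of subjects is affected. The documents do not support a share. The 42% and 46% follow from an assumed even spread of visits, and everyone being seen on the first permitted day is a limit, not a forecast.

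After Visit 8 the gap is softened by the hospitalization prompt, by passive SAE reporting and, at Visit 9, by a targeted examination based on complaints since the previous visit. That stands for Dose 3. After Visit 12, passive reporting is the main safeguard in the visible text. Section 8.2 also ends in a redacted block whose content cannot be judged.

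All groups share the same windows, the study is descriptive and the two stages are analysed separately, so neither bias between groups nor a distorted comparison of Dose 3 with Dose 4 is expected. That stands.

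On SAP 6.2.2 as written, Dose 4 SAEs are analysed only to 28 days, so the Visit 12 gap would not reach that table. True, but that conflicts with the endpoint, and resolving it in favour of 6 months would bring the gap in.

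On blinding, a reader might conclude that an early Visit 12 breaks the Dose 4 blind early. The documents do not say whether unblinding is per subject or study-wide; only the mismatch of the two markers is established.

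**Conclusion.** The mismatch is in the text and holds for the SAE endpoints. Active collection can end up to 13 days before 6 months after Dose 3 (16 if 6 months is 183 days) and up to 28 days before 6 months after Dose 4. With evenly spread visits, a 180-day cut, a constant event rate and no later capture, the average loss is 1.6% and 3.7% of the period, too small to change a reading of Table 8. Under a to-the-visit reading the average loss is about nil, but follow-up is uneven. The Dose 4 gap is the less protected of the two.

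The 28-day AE part is negligible. Understatement of event rates, a large affected share and between-group bias are not established. The 28-day Dose 4 SAE period in SAP 6.2.2 is a separate and larger inconsistency. Overall this is a cheap improvement, low to moderate in severity.

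**What to change.** 1. In Protocol 8.2, define 6 months as a number of days, and end active SAE reporting at the later of Visit 8 or Visit 12 and that day after Dose 3 or Dose 4.
2. At Visit 9 (6.1.9, 6.2.9 and, for extension entrants, 6.3.1) and Visit 13 (6.3.5), ask about SAEs with onset between the earlier visit and that day. Protocol 6.5 already has the investigator record SAEs since the last visit for withdrawn subjects who cannot attend at 12 months, so the question is workable.
3. State the same day cut-off in SAP 6.1.2 and 6.2.2.
4. Reconcile the 28-day Dose 4 SAE period in SAP 6.2.2 with SAP 3.2.2 and Protocol 2.2.4.
5. Reconcile the two markers for the Dose 4 blind in Protocol 5.2 and 5.3.

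The visit windows should stay as they are, because moving them would shift immunogenicity sampling. Raising the lower bounds for the 28-day AE period would also move the primary Month 7 draw.

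The cost is a few sentences and one CRF question at visits already scheduled. The downside is that a few events will be recalled at a later visit.

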### **8.3. Definition of an Adverse Event**

An AE is any untoward medical occurrence in a clinical investigation subject administered a product or medical device; the event need not necessarily have a causal relationship with the treatment or usage. Examples of AEs include but are not limited to:

- Abnormal test findings;
- Clinically significant symptoms and signs;
- Changes in physical examination findings;
- Hypersensitivity;
- Progression/worsening of underlying disease;
- Drug abuse;
- Drug dependency.

Additionally, they may include the signs or symptoms resulting from:

- Drug overdose;
- Drug withdrawal;
- Drug misuse;
- Drug interactions;
- Extravasation;
- Exposure during pregnancy (EDP);
- Exposure via breastfeeding;
- Medication error;
- Occupational exposure.

#### **8.4. Medication Errors**

Medication errors may result, in this study, from the administration of the wrong investigational product, to the wrong subject, at the wrong time, or at the wrong dosage strength. Such medication errors occurring to a study participant are to be captured on the medication error CRF, which is a specific version of the AE page, and on the SAE form when appropriate. In the event of medication dosing error, the sponsor should be notified immediately.

Medication errors are reportable irrespective of the presence of an associated AE/SAE, including:

- Medication errors involving subject exposure to the investigational product;
- Potential medication errors or uses outside of what is foreseen in the protocol that do or do not involve the participating subject.

Whether or not the medication error is accompanied by an AE, as determined by the investigator, the medication error is captured on the medication error version of the AE page and, if applicable, any associated AE(s) are captured on an AE CRF page.

Other examples include, but are not limited to:

- The administration of expired investigational product;
- The administration of an incorrect investigational product;
- The administration of an incorrect dosage;

- The administration of investigational product that has undergone temperature excursion from the specified storage range, unless it is determined by the sponsor that the investigational product under question is acceptable for use.

### **8.5. Abnormal Test Findings**

The criteria for determining whether an abnormal objective test finding should be reported as an AE are as follows:

- Test result is associated with accompanying symptoms; and/or
- Test result requires additional diagnostic testing or medical/surgical intervention; and/or
- Test result leads to a change in study dosing or discontinuation from the study, significant additional concomitant drug treatment, or other therapy; and/or
- Test result is considered to be an AE by the investigator or sponsor.

Merely repeating an abnormal test, in the absence of any of the above conditions, does not constitute an AE. Any abnormal test result that is determined to be an error does not require reporting as an AE.

### **8.6. Serious Adverse Events**

An SAE is any untoward medical occurrence at any dose that:

- Results in death;
- Is life-threatening (immediate risk of death);
- Requires inpatient hospitalization or prolongation of existing hospitalization;
- Results in persistent or significant disability/incapacity (substantial disruption of the ability to conduct normal life functions);
- Results in congenital anomaly/birth defect.
- Lack of efficacy in an approved indication should be reported as an SAE.

Medical and scientific judgment is exercised in determining whether an event is an important medical event. An important medical event may not be immediately life-threatening and/or result in death or hospitalization. However, if it is determined that the event may jeopardize the subject or may require intervention to prevent one of the other AE outcomes, the important medical event should be reported as serious.

Examples of such events are intensive treatment in an emergency room or at home for allergic bronchospasm; blood dyscrasias or convulsions that do not result in hospitalization; or development of drug dependency or drug abuse.

